7.6 Safety Monitoring

The NCCIH requires that all Human Subjects research studies undergo independent monitoring, and NCCIH Program Officials will provide specific guidelines to the PI for the study. According an Independent Monitoring Committee will be assembled by the PI with approval required by the NCCIH.

8. INTERVENTION DISCONTINUATION

Early Termination

The study doctor or the sponsor can stop a subject's participation at any time without their consent for the following reasons:

- If it appears to be medically harmful to them;
- If they fail to follow directions for participating in the study;
- If it is discovered that they do not meet the study requirements;
- If the study is canceled; or
- For administrative reasons, including competitive enrollment (e.g. the target number of subjects has entered the study.)
- If the patient's clinical condition worsens emergently as determined by physician.

9. STATISTICAL CONSIDERATIONS

9.1 General Design Issues

Primary Objective

The primary objective is to refine procedures for conducting a future fully powered multi-site RCT in 3 EDs.

Secondary Objectives

The secondary objectives of this study are to: examine the feasibility of data collection in the RCT, develop a responsive acupuncture intervention and assess implementation and treatment outcomes in emergency departments associated with 3 BraveNet research sites. This study will include qualitative interviews and structured observation to assess feasibility of implementation.

9.2 Sample Size and Randomization

Sample size justification for feasibility study

We justify the sample size of the proposed feasibility study by first considering the sample size that

would be required for the future UG3/UH3 multi-site non-inferiority RCT. Per NCCIH guidance⁷⁷ and the literature,⁷⁸⁻⁸⁰ we recognize that results from pilot/feasibility studies are not suitable for determining power. Rather clinically significant differences are required for the power calculation.⁷⁸⁻⁸⁰ The verbally administered NRS has been validated and a minimum clinically significant change for acute pain intensity has been shown range from 1.3 (95% CI 1.0, 1.5)^{65,81} to 2.0.

For non-inferiority trials it is more conservative to use the lower estimate of clinical significance. Following convention we divide the minimally reported clinically significant change by two⁸² to obtain a non-inferiority margin of 0.65 (=1.3/2). That is, to test whether Acupuncture group is at most 0.65 units inferior to the Usual Care group, a sample sizes of 510 (255 Acupuncture vs 255 Usual Care) will achieve 80% power to detect non-inferiority. We will use a one-sided Mann-Whitney test with type 1 error 0.05.

The power calculation is based on the assumption that pain improvement between the Acupuncture therapy and Usual Care groups is equivalent and that the actual score distributions are normal. We assumed a standard deviation of 2.52 for the Acupuncture group based on our previous collection of pain scores related to our previous single-site pilot acupuncture in the ED, and 3.2 for the Usual Care group, an estimate drawn from a study measuring effects of IV morphine at 60 minutes in the ED.⁹⁵ Using the same retention rate for the post-treatment PRO data collection of the pilot RCT (~78%), the target sample increases to a total sample size of 654 (327 Acupuncture vs 327 Usual Care) for a future UG3/UH3 efficacy RCT.

Since the goal of the current U01 proposal is to test feasibility of the study procedures used in the single-site pilot RCT, we plan to enroll 150 participants (50 per site). Additionally, a pilot 5 subjects per site will be consented and brought through the study protocol, but will not be counted toward the n=150 enrollment. The 150 enrollment number is both pragmatic for achieving our goals related to assessing feasibility, acceptability and fidelity and is about 25% of the eventual sample size required for a future definitive non-inferiority study. We contend that our ability to recruit about 25% of the anticipated sample size for a future definitive RCT would demonstrate our collective capabilities to recruit across 3 EDs across the United States..

Treatment Assignment Procedures

Random assignments will be made by the study statistician in permuted blocks of size 2 and 4. The block size will also be randomly generated to minimize correct prediction of assignments and preserve approximate balance between groups, using the rand function in SAS. Administrative personnel from the BraveNet Coordinating Center will prepare each randomization packet in a sealed envelope and send these to each site in batches. A date/signature label will be placed over the envelope seal. Randomization envelopes will be stored in locked cabinets and opened by study staff (SC or RA) after completion of the informed consent process and baseline data collection.

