Results: During the 7 month study period, the SC screened 418 patients for eligibility criteria, including but not limited to pain score ≥ 4 . Following screening, 59 were deemed eligible, and 46 consented and randomized to Acupuncture (n=23) or Usual Care (n=23) with 2 subjects in the Acupuncture group withdrawing after consent. The average age was 36.3 (15.5 SD), 78% were female and 55.0% were non-white. Those randomized to Acupuncture reported a pre-treatment pain score of 8.18 (SD 1.62), a 60-min post-treatment pain decrease of -3.0 units (SD 2.51), decrease at ED discharge of -2.71 units (SD 1.86) and reduction at 30-day follow-up of -5.28 (3.0) units. The Usual Care group had a pre-treatment pain score of 7.91 (SD 1.41), a 60-min post-treatment pain decrease of -1.56 units (SD 2.37), decrease at ED discharge of -2.53 units (SD 2.27) and reduction at 30-day follow-up of -3.41 (4.0) units. Since the aim of the pilot RCT was to determine feasibility, as a result no between-group analyses were conducted.

“Lessons learned” included that: (1) an RCT was feasible in a busy ED; (2) ~14% (59/418) of screened patients met eligibility criteria; (3) ~78% (46/59) of eligible patients consented to participate; (4) ~78% of both Acupuncture and Usual Care patients provided post-treatment and ED discharge scores; (5) electronic data collection was feasible for blinding the study team assessor to patient scores; but (6) only ~35% (16/46) of both groups completed the 30-day follow-up via phone call, so new methods for follow-up are needed.

Observational Study 2: University Hospitals (UH) Broadview Heights ED

Upon joining University Hospitals & Case Western Reserve University in Oct 2018, [name] launched a 4-week observational study to replicate/extend the procedures used in the ANW ED observational study (above). Changes included the use of auricular ear seeds to potentially extend pain relief, and reducing 30 day follow-up to a 1-week (+/- 2 days) phone call. Goals were to: (1) determine whether auricular ear seeds would be tolerated by patients; and (2) preliminarily explore if ear seeds provided extended pain relief at 1-week.

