9.5 Outcomes

Implementation and Treatment Outcomes

All data analyses will be preceded by extensive data checking and verification to identify and resolve the reasons for missing values, inconsistencies, and out-of-range values. Although we anticipate little missing data based on our experience, we will carefully examine whether missingness is completely at random, at random or informative. Models proposed for analysis can handle incomplete data but do

require at least that missingness be at random. Descriptive statistics of primary outcomes: pain intensity change scores for Pre-Treatment to Post-Treatment and Pre-treatment to ED Discharge as well as secondary outcomes will be conducted to assess their distribution overall and by sites as well as demographic characteristics (e.g. sex, age group, race, household income, pain location among others). The variables will be summarized using descriptive statistics (sample size, mean, standard deviation, median, minimum, and maximum) for continuous variables and by the number and percentage of patients for categorical variables. We will report 95% exact confidence interval of median⁸³ for the key continuous variables and 95% exact binomial confidence interval⁸⁴ for categorical variables. All assessments will include sex as a biological variable as described below.

Feasibility of Recruitment and Retention

We will assess recruitment rates (# enrolled / # eligible), pace of accrual, data completeness, and retention at each data collection point, overall and across sites. We will assess variables across different patient groups (including age, race, sex), and across the study arms. Provider adoption will be assessed by the proportion of their eligible patients that clinicians approve for study participation. We will assess variables across different provider characteristics (including age, race, sex), and across the study sites. Completeness of data collection and retention at each time point: we will also track completeness of data collection, and patterns and proportions of missing data at each time point. We will compare these proportions overall and across sites and by demographics as described above.

Acceptability

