 - a. No high school diploma
 - b. High school or equivalent
 - c. Education beyond high school, but have not completed a bachelor's degree
 - d. College degree
 - e. Graduate or professional degree
 - f. Decline to answer
7. What is your current marital status?
 - a. Married, spouse in household

- b. Married, spouse not in household
- c. Significant other or partner
- d. Widowed
- e. Divorced
- f. Separated
- g. Never married
- h. Decline to answer

8. What is your current employment status?

- a. Working full-time
- b. Working part-time
- c. Not employed due to other responsibilities (raising children, keeping house, student)
- d. Retired
- e. On medical leave or disabled
- f. Unemployed, looking for work
- g. Other [FREE TEXT]
- h. Decline to answer

9. What is the annual income of your household?

- a. Less than \$20,000
- b. \$20,000 to \$50,000
- c. \$50,001 to \$100,000
- d. \$100,001 to \$150,000
- e. More than \$150,000
- f. Decline to answer

10. Which of the following is your primary health insurance?

- a. Medicare
- b. Medicaid
- c. Other insurance
- d. No insurance
- e. Decline to answer

11. Approximately how much do you weight (in pounds)? [FREE TEXT]

12. What is your approximate height?

- a. Feet
 - i. 3
 - ii. 4
 - iii. 5
 - iv. 6
 - v. 7

- b. Inches
 - i. 0
 - ii. 1
 - iii. 2
 - iv. 3
 - v. 4
 - vi. 5
 - vii. 6
 - viii. 7
 - ix. 8
 - x. 9
 - xi. 10
 - xii. 11

SECTION 2 – Expectancy Questions Patient Facing, to be answered by the patient; blinded. Questions need to be presented as shown here in longitudinal fashion.

1. By the end of the treatment period in the ER, how much improvement in your pain symptoms do you **think** will occur?
 0% 10% 20% 30% 40% 50% 60% 70% 80% 90% 100% Unsure

Now, please close your eyes for a few moments and try to identify what you really **feel** about the treatment and its likely success. Then answer the following questions:

2. At this point, how much do you really feel that the treatment will help you to reduce your pain symptoms?

1	2	3	4	5	6	7	8	9
Not at all				Somewhat				Very much
								Unsure

3. By the end of your treatment period in the ER, how much improvement in your pain symptoms do you really **feel** will occur?
 0% 10% 20% 30% 40% 50% 60% 70% 80% 90% 100% Unsure

SECTION 3 – Pain

1. Please rate your pain, **right now**, on a scale of 0 to 10, where 0 is no pain, and 10 is the worst pain imaginable.

0	1	2	3	4	5	6	7	8	9	10
---	---	---	---	---	---	---	---	---	---	----

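### Does Section 9.2's 80% power fail because it does not say how a 0.65-point margin enters the Mann-Whitney test?

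*Combined protocol and SAP*

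**What the plan says.** Section 9.2 reasons from the size of a future multi-site non-inferiority RCT. It halves a minimum clinically significant change of 1.3 to get a margin of 0.65 NRS units, and the aim is "to test whether Acupuncture group is at most 0.65 units inferior to the Usual Care group". With 255 per arm the design "will achieve 80% power to detect non-inferiority", and the test is named in one sentence: "We will use a one-sided Mann-Whitney test with type 1 error 0.05". The calculation assumes equal improvement in the two arms and "that the actual score distributions are normal", with SDs of 2.52 (Acupuncture) and 3.2 (Usual Care). Allowing for 78% retention, the total becomes 654. The section then notes that 150 "is about 25% of the eventual sample size required for a future definitive non-inferiority study", and in the same sentence calls 150 a pragmatic number for assessing feasibility, acceptability and fidelity.

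For the present trial, Section 9.5 plans descriptive statistics on "pain intensity change scores for Pre-Treatment to Post-Treatment and Pre-treatment to ED Discharge". The pain item on the Appendix B forms is rated "on a scale of 0 to 10, where 0 is no pain, and 10 is the worst pain imaginable", with the whole numbers 0 to 10 as the response options.

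**The concern.** A Mann-Whitney test works on ranks and has no units. A margin of 0.65 points can only enter it through some further rule, such as shifting one arm's scores, inverting the test into a confidence limit for a location shift, or restating the margin as a probability that one arm's score exceeds the other's. Section 9.2 gives no rule, and no other section specifies a non-inferiority analysis of pain.

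The gap looks serious because of the scale. A difference between two whole-number ratings is a whole number, so adding 0.65 to one arm does nothing except break ties in its favour. The test could not then distinguish a margin of 0.65 from one of 0.01 or 0.99. If so, the future trial would have well under 80% power, its conclusion would not refer to 0.65 points, and one of the two stated reasons for enrolling 150 would rest on too small a target.

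**Working it through.** **1. Inputs, all from Section 9.2.** Margin 0.65; true difference 0; SDs 2.52 and 3.2; one-sided alpha 0.05; power 80%; 255 per arm; retention 78%.

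**2. The plan's figures.** The sum of variances is 2.52² + 3.2² = 6.35 + 10.24 = 16.59.

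- Comparison of means: n per arm = (1.645 + 0.842)² × 16.59 / 0.65² ≈ 242.8.
- Mann-Whitney efficiency under normality is 3/π = 0.955, so 242.8 / 0.955 = 254.2, which rounds up to 255.
- Power at 255: the standard error is √(16.59 / (255 × 0.955)) = 0.261, and Φ(0.65/0.261 − 1.645) = 0.80.
- Retention: 255 / 0.78 = 326.9, so 327 per arm and 654 in total. Then 150/654 = 0.229.

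Simulating continuous normal scores with a 0.65 shift gives 80-81% power. The stated figures are correct on the stated assumption.

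**3. The shift reading with whole-number scores.** For integers X and Y and any shift s strictly between 0 and 1, X + s > Y exactly when X ≥ Y. All such shifts therefore give the same ranks. In one simulated data set p was 0.0880 at shifts of 0.01, 0.30, 0.50, 0.65 and 0.99, and 0.0005 at 1.0. The test behaves as if the margin were about 0.5:

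- Power: Φ(0.5/0.261 − 1.645) = 0.607.
- Size for 80% power: 254.2 × (0.65/0.5)² = 430 per arm, or 860. With retention, 860/0.78 = 1,103, and 150/1,103 = 0.136.

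**4. Simulation.** Normal changes with the plan's SDs were rounded to whole numbers, with 255 per arm and several thousand trials per run.

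| Way of applying the margin | Power | Rejection at a true 0.65 deficit |
|---|---|---|
| Shift by 0.65 and re-rank | 60-62% | 1.2-1.6% |
| Rank-effect margin, Φ(0.65/√16.59) = 0.563, ties counted half | 80% | 5.3% |
| Random tie-breaking, then shift | 79% | 5.4% |
| Welch difference in means | 81-82% | 4.5-5.1% |

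**5. Scores bounded at 0-10.** This needs a baseline that Section 9.2 does not give. The value assumed is 8.0 (SD 1.5), close to the pilot RCT in Section 2.2, whose Usual Care arm "had a pre-treatment pain score of 7.91 (SD 1.41), a 60-min post-treatment pain decrease of -1.56 units". Observed SDs were held at 2.52 and 3.2, and mean improvement was assumed to be 2.0, 2.5 or 3.0.

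| Method | Power | Rejection at a 0.65 mean deficit |
|---|---|---|
| Shift and re-rank | 72%, 65%, 56% | 3.8%, 2.5%, 1.2% |
| Rank-effect margin 0.563 | 89%, 85%, 78% | 11.0%, 8.5%, 6.1% |
| Welch | 82%, 82%, 81% | 5.2%, 5.1%, 5.4% |

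If the bounds are instead allowed to shrink the SDs, to about 2.3 and 2.8, the shift version gives 65-68%.

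**The case for a change.** The best case for a change is that the gap is real and the affected reading is not exotic. Shifting scores, or inverting the test into a Hodges-Lehmann limit, are the usual ways to combine a margin in scale units with this test. With whole-number data the limit is built from whole-number pairwise differences, so comparing it with 0.65 is no different from comparing it with any other value between 0 and 1. Both routes fail in the same way. Section 1.1 makes refining procedures for the fully powered RCT the primary objective, so that trial's power is not irrelevant here, and a single sentence would settle the matter.

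The mechanism stands, and so does the omission. What does not follow is that a figure in the plan is wrong or that this protocol needs amending. Section 9.2 states its normality condition openly, and its figures are right under it. The shortfall appears only once a procedure is supplied that the plan does not state. Even then the error runs in the cautious direction, with about 1.5% rejection at a true 0.65 deficit against a nominal 5%, so no false claim of non-inferiority is invited. The whole-number premise comes from the present trial's forms, and using the same item in the later trial is an inference.

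Nor is every replacement rule free of cost. The rank-effect margin holds 80% power on unbounded scores, but in the bounded runs it rejects 6-11% of the time at a 0.65 mean deficit. That choice deserves proper consideration in the later trial's analysis plan.

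**Conclusion.** No change to the plan. Section 9.2 leaves out a detail of a test that this trial does not run. The 255 per arm, 654 in total and 80% power reproduce exactly under the stated SDs and normality. A statistician analysing whole-number pain changes against a margin in points would ordinarily compare mean changes with a one-sided 95% limit, which keeps about 81-82% power at 255 per arm. With that choice, 654 and the ratio of 150 to it, about 23%, also stand.

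The unfavourable case is a plain shift with re-ranking. It gives about 61% power under the plan's SDs and rounding alone. The roughly 56-72% range for bounded scores depends on an assumed baseline, an assumed improvement and whether the SDs are held fixed. Only if that version were knowingly kept would the later trial need about 430 per arm, making 150 about 14% of it.

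For the current trial nothing turns on this. Its primary outcomes are recruitment and retention (Section 3), its pain summaries are descriptive (Section 9.5), and 150 has its own pragmatic justification. The place to say how the margin and ties are handled is the analysis plan of the future RCT.

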9.3 Definition of Populations

N/A

9.4 Interim Analyses and Stopping Rules

N/A

9.5 Outcomes

Implementation and Treatment Outcomes

All data analyses will be preceded by extensive data checking and verification to identify and resolve the reasons for missing values, inconsistencies, and out-of-range values. Although we anticipate little missing data based on our experience, we will carefully examine whether missingness is completely at random, at random or informative. Models proposed for analysis can handle incomplete data but do

require at least that missingness be at random. Descriptive statistics of primary outcomes: pain intensity change scores for Pre-Treatment to Post-Treatment and Pre-treatment to ED Discharge as well as secondary outcomes will be conducted to assess their distribution overall and by sites as well as demographic characteristics (e.g. sex, age group, race, household income, pain location among others). The variables will be summarized using descriptive statistics (sample size, mean, standard deviation, median, minimum, and maximum) for continuous variables and by the number and percentage of patients for categorical variables. We will report 95% exact confidence interval of median⁸³ for the key continuous variables and 95% exact binomial confidence interval⁸⁴ for categorical variables. All assessments will include sex as a biological variable as described below.

Feasibility of Recruitment and Retention

We will assess recruitment rates (# enrolled / # eligible), pace of accrual, data completeness, and retention at each data collection point, overall and across sites. We will assess variables across different patient groups (including age, race, sex), and across the study arms. Provider adoption will be assessed by the proportion of their eligible patients that clinicians approve for study participation. We will assess variables across different provider characteristics (including age, race, sex), and across the study sites. Completeness of data collection and retention at each time point: we will also track completeness of data collection, and patterns and proportions of missing data at each time point. We will compare these proportions overall and across sites and by demographics as described above.

Acceptability

At ED discharge, 1-week and 4-week follow-up, all participants will be asked to answer; “How satisfied are you with how your pain was managed during your ED visit” on the 5-point Likert scale. A second question is “Overall how satisfied are you with your treatment during your ED visit?” on the same Likert Scale. At the end of enrollment, the SC or RA at each site will contact ED staff to complete a brief survey (via REDCap) to assess their general satisfaction with the acupuncture intervention by answering “Do you view acupuncture in general as an appropriate intervention for the ED setting?” Likert scale (1-very appropriate—5-Very inappropriate) and “Do you view acupuncture in general as helpful in managing patient pain in the ED?” Likert scale (1-Very helpful—5- Not at all helpful). *And two questions regarding the delivery of ACUITY study in the ED:* “Were you satisfied with how the ACUITY acupuncture intervention was delivered in your setting?” Likert scale (1-Very satisfied—5-Very dissatisfied) and “Did the ACUITY project impose a burden on ED staff in your setting?” Not a burden, Somewhat of a burden, Moderate burden, Extreme burden. We will compare across sites and across patient groups (e.g. pain location, patient demographics etc). We will calculate the proportion of subjects answering each question and 95% exact CI across sites as well as across patient groups such as different presenting complaints and patient demographics. We will assess variables across different provider characteristics (including age, race, sex), and across the study sites.

Fidelity

Assessing fidelity will reveal proportion of patients who are treated in a manner consistent with the manualized intervention and treatment fidelity parameters determined by consensus of acupuncture experts in accord with Aim 1. We expect that the treatment fidelity measures will include: the dose (minimum number of needles, minimum points treated, minimum duration of needle retention time), and the delivery (was the intervention delivered as planned or cut short due to ED flow).⁸⁵ [name] will review the documentation of all acupuncture interventions and assess manual fidelity. She will assess the proportion of cases where acupuncturists treated the patient ‘off manual’ (and why), as well as assessing whether minimum standards for number of needles used, points treated and needle retention time were met. Assessment will be across different practitioners, times of day, sites, and by participant demographics (e.g. sex and pain complaints).

Qualitative Analysis

Drs. [name] and [name] have collaborated frequently, using large, mixed methods data sets to bring together implementation data and conduct detailed analyses. To analyze interview and observational

data, we will use QSR's NVivo, a computer program that facilitates 1) the rapid organization and retrieval of thematically linked data; and 2) the use of quantitative grouping variables to classify cases and generate complex comparisons. In a first step of thematic analysis, a preliminary coding scheme will be developed and applied to a subset of the data and then revised as needed. This process will be repeated on subsets of data until it is judged sufficiently accurate and comprehensive. Data will be uploaded into NVivo and coded. Memos will be created for each interview describing the major themes emerging in the transcript. Next, coded data will be retrieved and used to create case summaries of key themes related to implementation processes at each site. Quantitative implementation outcome data collected in Aim 2 will be used where relevant to create groups for the purpose of comparison. Within site analyses will include comparisons of relevant groups (e.g. comparing perceptions of the intervention across different genders and ethnic groups; patients who achieve satisfactory pain relief vs those who do not; providers who are more vs less satisfied with the protocol, among others). In the cross site analyses, we will examine differences in barriers, facilitators and implementation processes across sites with the goal of generating inferences regarding the important factors shaping differences in implementation outcomes (e.g. presuming that sites differ on rates of recruitment, examining our qualitative data to generate hypotheses regarding the causes of this documented difference).

Potential Challenges and Alternate Strategies

As noted above, we expect to recruit 50 subjects (+ 5 pilot subjects) in 9 months of active enrollment at each site. Results from our pilot RCT indicate a 78% enrollment rate. Using more conservative estimates of eligible patients consenting to participate (e.g. 50%), we would still have ample opportunity to recruit enough patients in 9 months/site. However, if recruitment lags, we can extend the duration of recruitment by 3 months or increase the number of enrollment hours per week at each site.

